### **6.2. Inclusion criteria**

- Treated for EC with a curative resection between 2000 and 2012
- Age  $\geq 18$  years
- Written informed consent
- No signs of tumor recurrence or new other malignancies.

### **6.3. Exclusion criteria**

- Thoracic radiotherapy for indications other than EC.
- Contra indication for cardiac MRI, pacemaker, cochlear implants, metal not compliant with MRI.

## 7. SAMPLE SIZE CALCULATION

As this is a pilot study to determine (sub-clinical) cardiopulmonary toxicity, a total of 40 patients, 20 in each group, will be included in this study.

## 8. METHODS

### 8.1. Randomisation, blinding and treatment allocation

Not applicable

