#### *Patient population*

As many of our EC patients are older and have cardiopulmonary problems as a result of their age, co-morbidities or lifestyle habits, we would like to compare a cohort of patients treated for EC who did or did not undergo (chemo)radiotherapy.

A cohort of these patients is available, as neo-CRT has become standard treatment since 2012 after the publication of the so-called CROSS trial, demonstrating an important survival benefit in the group that received neo-CRT followed by surgery compared to patients treated with surgery alone. During this time period and the time period shortly before and after, patients were treated either with or without neo-CRT. In this time period we did not select patients on cardiopulmonary co-morbidities or age, so we expect comparable groups. Part of these patients were already retrospectively analyzed and compared on short term (within 90 days) morbidity and mortality after resection [23]. These data were published in 2013. We demonstrated an increased incidence of pneumonia and rhythm disorders in patients treated with neo-CRT, but no difference was noted in neither hospital and intensive care unit stay nor in mortality or overall morbidity between these two groups. As these patients were treated in the time period 2000-2012 and thus will have a 5-15 years follow up there is a sufficiently large patient cohort available to prospectively analyze clinical and subclinical cardiac changes and/or toxicities.

*Which tests would be interesting at longer follow up or study parameters*

As mentioned in the introduction, the main focus of this study is (subclinical) cardiopulmonary (dys)functioning. The most important late (subclinical) toxicities we expect to find at longer follow up are: diastolic dysfunction, coronary artery disease, cardiac wall motion disorders, heart failure, pulmonary hypertension, pericardial effusion and/or constriction, cardiac arrhythmia and valve disorders. A number of these endpoints will eventually result in heart failure.

- Anamnesis and physical examinations will be performed in these patients
- In case a pulmonologist or cardiologist has been consulted, additional information will be collected from hospital records of these specialists.
- Radiotherapy treatment parameters will be collected from our database in case the patient was treated with radiotherapy.
- 6 minute walking test
- Echocardiogram
- CT scan
- Cardiac MRI scan
- ECG

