### **3. ENDPOINTS**

As this is an exploratory pilot study to determine the most suitable diagnostic tests for future studies, there will be several endpoints related to (sub)clinical cardiopulmonary dysfunction. Signs of myocardial ischemia, systolic or diastolic dysfunction, rhythm and valve disorders, pericardial effusion and fibrosis, myocardial fibrosis, focal wall motion disorders and coronary calcifications will be analyzed.

The cardiopulmonary (dys)function in EC survivors treated with neo-CRT followed by surgical resection will be compared to cardiopulmonary (dys)function in EC survivors treated with surgical resection alone.

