## **6. STUDY POPULATION**

### **6.1. Population (base)**

Patients with EC treated with or without neo-CRT, alive without evidence of disease, treated between 2000 and 2012 at the University Medical Centre Groningen will be eligible. Twenty patients will be included in both treatment groups. Length of follow up after treatment does not seem to be an important confounding factor as surgery is not considered to be an important risk factor for late toxicity.

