#### *6 minute walking test:*

Gives an estimate of the general functioning status of the patients during follow up. It is known to correlate with maximum oxygen uptake and physical fitness without laboratory test [24].

*Laboratory tests:*

NT pro BNP and hs TNT are known markers in cardiology for myocardial damage and “volume overload” like in diastolic dysfunction. Blood markers like cholesterol, CRP, HbA1 will help determining the baseline risk on cardiac events. eGFR will be checked before gadolinium is infused in order to minimize risks on its possible side effects. It is necessary to determine hematocrit for calculation of the extracellular volume (ECV).

*ECG*

Simple screening instrument to indicate hypoxia, pericarditis, past infarctions, bundle branch blocks and rhythm disorders

*Echocardiogram:*

An echocardiogram is performed as a safe non-invasive screening technique, which is able to measure hypertrophy of the myocardium, pericarditis, wall motion disorders, blood flows and pressures, which are functional parameters who could indicate pulmonary hypertension and diastolic- or systolic dysfunction and valve disorders[25].

The echocardiographic assessment will be performed by the Echocardiography Core lab ([www.G-ICL.com](http://www.G-ICL.com)) facility, of the UMCG. The echocardiographic protocol includes assessments of systolic and diastolic function of both ventricles according to the guidelines of the European Association of Cardiovascular Imaging (EACVI). Specifically we will assess:

1. Tricuspid annular plane systolic excursion (Tapse)
2. Velocity of the tricuspid annular systolic motion (RV s')
3. Right ventricle fractional area change
4. Doppler notching of right ventricular outflow tract signal
5. Tricuspid valve Doppler velocity
6. Pulmonary valve Doppler velocity
7. Myocardial performance index (Tei index)
8. Pulmonary artery acceleration time
9. Pulmonary valve end diastolic velocity
10. Cardiac Output
11. Left ventricle systolic function

- 12.Left ventricle diastolic dysfunction
- 13.Valvar abnormalities
- 14.Left ventricle eccentricity index
- 15.Right ventricle strain
- 16.Right atrium volume
- 17.Inferior Caval Vein collapsibility

Also 2D strain echocardiography will be performed to establish subtle changes in myocardial function.

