#### Cardiac CT imaging :

CT imaging will be performed on a latest generation dual-source CT scanner (Siemens Medical Solutions, Forchheim, Germany). A non-enhanced CT high pitch spiral acquisition in diastole with prospective electrocardiography (ECG) triggering will be performed with a standard protocol (120 kV tube potential; ref mAs 75) with an associated radiation dose of 0.6 mSv (less than a third of the annual background radiation dose). On the CT acquisition, the amount of coronary calcification will be calculated and expressed as a Coronary Artery Calcium (CAC) score based on the Agatston method.

The CAC score can be used to compare the current and baseline status (using the diagnostic CT scans performed before treatment) and is a reliable instrument for coronary disease [26]. Furthermore, dose distributions can be correlated with the coronary artery calcifications by fusing diagnostic CT scans with the planning CT scans in irradiated patients.

The CAC score at baseline will be used to estimate the baseline risk on cardiac events

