#### Cardiac MRI:

Cardiac MRI will be performed with a 1.5- or 3.0-Tesla MRI scanner (Siemens Medical Solutions, Forchheim, Germany). Imaging is performed during breath-hold at end-expiration. During the procedure, ECG is continuously monitored. After acquisition of scout views for the determination of the standard orientations of the heart, cine images will be acquired for functional evaluation and measurements (4 chamber, 2 chamber, short axis). T1 acquisitions are performed before and after injection of 0.2 mmol/kg gadoterate meglumine (Dotarem, Guerbet, Villepinte, France). T1 mapping is a parametric quantitative sequence, which provides tissue-specific T1 values. For T1 mapping, a 5(3)3 sampling scheme of the heart is performed,

using a modified Look Locker sequence. Pixel-wise T1 maps of the myocardium are acquired in 3 short-axis views with inline motion correction. The major advantage of T1 mapping sequences is their potential for quantitative objective assessment of myocardial abnormalities. Myocardial pathologies leading to T1 changes include diffuse myocardial fibrosis, edema, inflammation, and infiltrative diseases such as amyloidosis, Fabry disease, and hemosiderosis. The comparison of T1 values before and after Gadolinium enable the quantitative estimation of myocardial interstitial remodeling and extracellular space expansion, to evaluate myocardial extracellular volume. Ten minutes after the Gadolinium injection, a late Gadolinium enhancement (LGE) series is performed to assess possible myocardial infarction and gross fibrosis. Image post-processing includes the measuring of cardiac dimensions, ventricular volumes, LV and RV function, LV mass, and T1 tissue values.

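### Section 8.1 dismisses blinding as not applicable, so ECG, echo, CT and MRI are read with no stated masking to treatment group, and visually judged findings are open to expectation bias

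*Protocol*

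**What the plan says.** Section 8.1 puts three topics under one heading, "Randomisation, blinding and treatment allocation", and disposes of all three as not applicable.

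The outcome tests are done and read in the study (Section 8.2):

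- ECG: "Simple screening instrument to indicate hypoxia, pericarditis, past infarctions, bundle branch blocks and rhythm disorders".
- Echo: "The echocardiographic assessment will be performed by the Echocardiography Core lab" of the treating centre. The list of 17 items is mostly measurements but includes valve abnormalities, and the section also gives echo the detection of pericarditis and wall motion disorders.
- MRI: cine series for function, T1 mapping, and a "late Gadolinium enhancement (LGE) series is performed to assess possible myocardial infarction and gross fibrosis".
- CT: a calcium score by the Agatston method. Coronary calcification is related to dose by "fusing diagnostic CT scans with the planning CT scans in irradiated patients", and the radiotherapy plan subsection also co-registers the study's cardiac CT to the planning CT.

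Section 3 lists signs of ischaemia, rhythm and valve disorders and more, ending with "pericardial effusion and fibrosis, myocardial fibrosis, focal wall motion disorders and coronary calcifications will be analyzed", and compares the two treatment groups. Section 10.2 adds a descriptive table of where wall abnormalities and arteriosclerosis lie relative to high-dose regions.

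Section 12.6 assigns consecutive study numbers, with the code held by data management. Its stated purpose is privacy, and it covers files used for analysis.

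**The concern.** Blinding of treatment is moot here, but masking of outcome readers is a separate matter. It is feasible because every test is done once, long after treatment. The protocol does not provide for it, and a later analysis plan could not mask readings already made.

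The direction of any lean is foreseeable. Section 1 (Background) treats cardiopulmonary toxicity as the likely cause of excess deaths after thoracic radiotherapy. Section 1 (Patient population) opens a list with "The most important late (subclinical) toxicities we expect to find at longer follow up are" and includes wall motion, pericardial and valve disorders. Section 6.1 adds that "surgery is not considered to be an important risk factor for late toxicity". A reader who knows that a patient was irradiated has reason to resolve an equivocal image toward abnormal.

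At stake are the non-randomised comparison of 20 with 20 and, through it, the choice of tests. Section 11.4 carries the most promising tests and endpoints into a later cohort. A visual finding inflated in one group could make its test look more discriminating than it is.

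**Working it through.** **Is there masking elsewhere?** The possible safeguards, taken in turn:

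- *Echo core lab (8.2):* named, but not said to be kept unaware of treatment.
- *Study numbers (12.6):* a consecutive number does not reveal the group, but no section says that images are read under it or without the clinical history.
- *Order of reading and dose mapping (8.2, 10.2):* no section has lesion locations recorded before dose is seen.

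**Which outputs are exposed?**

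- *Exposed:* valve disorders, pericardial effusion and fibrosis, fibrosis on late enhancement, focal wall motion.
- *Less exposed:* calcium score, T1 and extracellular volume, ventricular volumes, Doppler velocities, strain. These make up most of what the t-test in Section 10.1 suits.
- *Not affected:* laboratory markers.
- *Dose-location table:* only CT is fused with the planning CT, so fusion exposes the location of coronary calcium. Wall motion comes from echo and cine MRI, which are not fused. Its location is exposed only if the reader knows the treatment or dose plan.

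**Size.** The plan gives no figure to reproduce. From Section 7, n = 20 per group, so one over-called scan shifts the difference by 1/20 = 5 percentage points.

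The rest is illustration, because the documents give neither over-call rates nor prevalences. Assume the same true prevalence p in both groups. Assume normal scans are over-called at rate f = 10% or 20% when irradiation is known, and at 5% otherwise.

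- Observed prevalence = p + (1 − p) × over-call rate.
- Spurious difference d = (1 − p) × (f − 0.05).
- SE = √{[a(1 − a) + b(1 − b)]/20}, where a and b are the observed prevalences.

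| p | f | Irradiated (a) | Surgery alone (b) | d | Scans of 20 | SE | d/SE | 1.96 × SE |
|---|---|---|---|---|---|---|---|---|
| 0.10 | 0.10 | 0.190 | 0.145 | 0.045 | 0.9 | 0.118 | 0.38 | 0.231 |
| 0.10 | 0.20 | 0.280 | 0.145 | 0.135 | 2.7 | 0.128 | 1.06 | 0.250 |
| 0.20 | 0.10 | 0.280 | 0.240 | 0.040 | 0.8 | 0.139 | 0.29 | 0.272 |
| 0.20 | 0.20 | 0.360 | 0.240 | 0.120 | 2.4 | 0.144 | 0.84 | 0.282 |
| 0.30 | 0.10 | 0.370 | 0.335 | 0.035 | 0.7 | 0.151 | 0.23 | 0.296 |
| 0.30 | 0.20 | 0.440 | 0.335 | 0.105 | 2.1 | 0.153 | 0.69 | 0.300 |

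By normal approximation, the chance that one such finding reaches two-sided 5% significance is 1 − Φ(1.96 − d/SE) + Φ(−1.96 − d/SE). This runs from about 6% (d/SE = 0.23) to about 18% (d/SE = 1.06).

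A harsher assumption gives more. If 10% to 30% of true negatives are over-called in the irradiated group and none in the other, the spurious difference is 7 to 27 points. The rejection rate of a two-sided Fisher test is then 4% to 41%, against 1% to 3% with no over-calling. The result follows the assumption, which is why no size can be claimed.

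**The case against.** The strongest reply is that this argues from silence. Not applicable is a natural answer to a combined heading in a non-randomised study of past treatment, and reading procedures may sit in a lower-level document. A reader might infer that the protocol has decided on unmasked reading, or that readers do know the group. The text supports neither. What stands is narrower: the section that names blinding closes the matter, no other section provides masking, and the protocol refers to no reading manual.

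Second, the expectation is pieced together. The list of expected toxicities names no group, and the same section attributes cardiopulmonary problems in these patients to age, co-morbidity and lifestyle. One might also infer from Section 6.1 that no late toxicity is expected after surgery; it says only that surgery is not an important risk factor. Even so, the toxicity hypothesis in Section 1 is about radiation, so the direction stands.

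Third, one might infer that fusion compromises the whole location table. It does not, because only CT is fused. The table is also descriptive, with no test.

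Fourth, most of what Section 10.1 would test is measured, and the assumed bias lies within the chance error of one finding. That is correct and limits the reach. It does not remove the point: chance error varies in sign between findings, whereas a shared expectation would tend to push the visual findings the same way. That tendency is an argument, not something the documents demonstrate.

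Fifth, the protocol does not say who reads ECG, CT or MRI. If clinical reporting uses the history, a separate masked reading may be needed, so the absence of extra reading effort cannot be assumed.

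**Conclusion.** The point holds in limited form. Section 8.1 leaves outcome reading unmasked by omission, and a defined set of visually judged endpoints is open to expectation bias toward the irradiated group. In the dose-location table, fusion exposes coronary calcium location only; wall-motion location is exposed only through knowledge of treatment or dose plan.

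The one figure that follows from the protocol is 5 points per over-called scan. The 3.5 to 13.5 points (0.7 to 2.7 scans of 20; 0.2 to 1.1 standard errors; 95% half-width 23 to 30 points) rest wholly on assumed over-call rates and prevalences. It would be tempting to conclude that the group comparison is biased by a known amount, or that the wrong tests will be chosen. The documents do not support either.

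The change should be made, because masking cannot be added after reading without re-reading. Confidence is medium.

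**What to change.** Limit not applicable in Section 8.1 to randomisation, treatment allocation and blinding of treatment, since treatment preceded the study. Then add a paragraph on outcome reading:

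- The planned readers do the offline research reading of ECG, echo, CT and MRI under the study number of Section 12.6, with treatment group and dose plan withheld.
- Coronary and wall-motion locations are recorded and locked before they are related to the dose distribution, and before any diagnostic or cardiac CT is fused with the planning CT.
- Treatment group is linked at analysis.
- The limits are stated: live echo acquisition is not masked, and images may reveal prior treatment.

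The research reading must be made consistent with the reporting and referral route in Section 8.2, which stays unchanged.

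The change is cheap: one paragraph and study numbers that already exist. It costs relabelling of scans for the reading list, a lock step before fusion and, if clinical reports are made with the history in view, a separate masked reading. Masking will be imperfect, so some exposure of valve and wall-motion findings will remain.

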### 8.2. Study procedures

Candidates will be selected from the surgical and radiotherapy database. General practitioners will be checked for their survival status. An introduction letter, including patient information for this study, will be sent to the surviving patients to explain the study and ask them to consider participation in this research project. Patients are given the opportunity to call the researcher for further information and questions about the study. Patients can give their informed consent by sending the written informed consent. After receiving the informed consent, appointments will be made whenever possible on one day in consultation with the patient.

- Interview and physical examination 45 minutes
- 6 minute walking test plus explanation 30 minutes
- ECG 15 minutes
- Laboratory tests 5 minutes
- Echocardiogram 30 minutes
- Cardiac CT scan 10 minutes
- Cardiac MRI scan 40 minutes

#### *Anamnesis and physical examination:*

The patients will be interviewed on matters concerning their medical history, cardiopulmonary complaints and patients will be asked to fill in the following questionnaires: EORTC ACE27, EORTC LC13, EuroQOL 5D and the EORTC C30. A general physical examination will be performed, including length and weight.

#### *6 minute walking test:*

Gives an estimate of the general functioning status of the patients during follow up. It is known to correlate with maximum oxygen uptake and physical fitness without laboratory test [24].

*Laboratory tests:*

NT pro BNP and hs TNT are known markers in cardiology for myocardial damage and “volume overload” like in diastolic dysfunction. Blood markers like cholesterol, CRP, HbA1 will help determining the baseline risk on cardiac events. eGFR will be checked before gadolinium is infused in order to minimize risks on its possible side effects. It is necessary to determine hematocrit for calculation of the extracellular volume (ECV).

*ECG*

Simple screening instrument to indicate hypoxia, pericarditis, past infarctions, bundle branch blocks and rhythm disorders

*Echocardiogram:*

An echocardiogram is performed as a safe non-invasive screening technique, which is able to measure hypertrophy of the myocardium, pericarditis, wall motion disorders, blood flows and pressures, which are functional parameters who could indicate pulmonary hypertension and diastolic- or systolic dysfunction and valve disorders[25].

The echocardiographic assessment will be performed by the Echocardiography Core lab ([www.G-ICL.com](http://www.G-ICL.com)) facility, of the UMCG. The echocardiographic protocol includes assessments of systolic and diastolic function of both ventricles according to the guidelines of the European Association of Cardiovascular Imaging (EACVI). Specifically we will assess:

1. Tricuspid annular plane systolic excursion (Tapse)
2. Velocity of the tricuspid annular systolic motion (RV s')
3. Right ventricle fractional area change
4. Doppler notching of right ventricular outflow tract signal
5. Tricuspid valve Doppler velocity
6. Pulmonary valve Doppler velocity
7. Myocardial performance index (Tei index)
8. Pulmonary artery acceleration time
9. Pulmonary valve end diastolic velocity
10. Cardiac Output
11. Left ventricle systolic function

- 12.Left ventricle diastolic dysfunction
- 13.Valvar abnormalities
- 14.Left ventricle eccentricity index
- 15.Right ventricle strain
- 16.Right atrium volume
- 17.Inferior Caval Vein collapsibility

Also 2D strain echocardiography will be performed to establish subtle changes in myocardial function.

#### Cardiac CT imaging :

CT imaging will be performed on a latest generation dual-source CT scanner (Siemens Medical Solutions, Forchheim, Germany). A non-enhanced CT high pitch spiral acquisition in diastole with prospective electrocardiography (ECG) triggering will be performed with a standard protocol (120 kV tube potential; ref mAs 75) with an associated radiation dose of 0.6 mSv (less than a third of the annual background radiation dose). On the CT acquisition, the amount of coronary calcification will be calculated and expressed as a Coronary Artery Calcium (CAC) score based on the Agatston method.

The CAC score can be used to compare the current and baseline status (using the diagnostic CT scans performed before treatment) and is a reliable instrument for coronary disease [26]. Furthermore, dose distributions can be correlated with the coronary artery calcifications by fusing diagnostic CT scans with the planning CT scans in irradiated patients.

The CAC score at baseline will be used to estimate the baseline risk on cardiac events

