## **2. OBJECTIVES**

Primary Objectives:

The main objective of this study is to determine the most suitable diagnostic test to identify cardiopulmonary (dys)function in EC survivors treated with neo-CRT followed by surgical resection. Furthermore, we want to estimate the difference in cardiopulmonary (dys)function in EC survivors treated with neo-CRT followed by surgical resection compared to EC survivors who were treated with surgical resection alone.

1. To determine the differences in clinical cardiac and pulmonary events, (cardiac ischaemia, heart failure, arrhythmia, valve disorders, pulmonary hypertension, COPD) as clinically diagnosed since treatment between patients treated with neo-CRT and surgery alone.
2. To determine the difference in other (subclinical) parameters as tested by echo cardiogram, 6 minute walking test, CT scan, MRI scan and biomarkers.
3. To analyse the current CAC scores in both patient groups.
4. To determine the difference between the baseline and current CAC scores.

5. To determine the difference between ECG findings currently and on baseline.
6. To correlate the different subclinical imaging parameters to the radiation dose given to the heart and lungs
7. To correlate CAC scores with the given dose distribution on plannings CT scan

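### The change in coronary calcium under objective 4 compares two kinds of CT that the protocol does not show to be comparable

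*Protocol*

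**What the plan says.** Section 2 of the protocol lists, as the fourth item under the primary objectives: "To determine the difference between the baseline and current CAC scores".

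Section 8.2 (Cardiac CT imaging) describes the current measurement in detail. On the scanner: "CT imaging will be performed on a latest generation dual-source CT scanner". On the acquisition: "A non-enhanced CT high pitch spiral acquisition in diastole with prospective electrocardiography (ECG) triggering will be performed with a standard protocol", at 120 kV. On the scoring: "On the CT acquisition, the amount of coronary calcification will be calculated and expressed as a Coronary Artery Calcium (CAC) score based on the Agatston".

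For the baseline measurement the same section gives only this: "The CAC score can be used to compare the current and baseline status (using the diagnostic CT scans performed before treatment". It adds that the baseline score will also serve to estimate baseline cardiac risk.

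The age of the baseline scans follows from section 6.2: "Treated for EC with a curative resection between 2000 and 2012".

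The protocol does not say how the old diagnostic scans were acquired. It sets no requirement on contrast, gating or slice thickness, and it describes no calibration, common score or restriction to comparable scans.

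**The concern.** A difference between two measurements is a change in the patient only if both measure the same quantity on the same scale. Here one is made to a fixed specification on a modern scanner, and the other comes from whatever diagnostic CT happened to exist years earlier. The Agatston method counts calcium by a density threshold, so contrast in the blood pool, slice thickness and cardiac motion can all alter the score while the calcium stays the same. A patient with stable calcium could appear to progress or to regress.

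Two uses are at stake: the within-patient change in objective 4, and the baseline CAC as a marker of prior cardiac risk. The pilot is meant to choose tests for a later prospective cohort, so a misleading CAC change could also misdirect that choice.

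**Working it through.** The protocol gives no CAC mean, SD, effect size or power, so there is no figure to reproduce. The check sets the two measurements side by side and then illustrates what a method difference could do. All values in steps 2 to 4 are assumptions, except the group size of 20 and total of 40 (section 7).

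**1. The two measurements as the protocol defines them**

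| Property | Current CT | Baseline CT |
|---|---|---|
| Scanner | latest-generation dual-source | not stated |
| Contrast | none | not stated |
| ECG triggering | prospective, diastole | not stated |
| Tube voltage | 120 kV | not stated |
| Slice thickness | not stated | not stated |
| Score | Agatston | not stated |

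If the baseline is also scored by Agatston, a threshold score is applied to uncontrolled acquisitions. If another score is used, objective 4 subtracts different scales. Either way, comparability is not secured.

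**2. Mechanism: averaging within a slice**

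Assume a scoring threshold of 130 Hounsfield units (HU), a background of 40 HU and a plaque 1.5 mm thick. Mean density = (plaque HU × plaque mm + 40 × remaining mm) / slice mm.

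- 300 HU plaque, 5 mm slice: (300 × 1.5 + 40 × 3.5) / 5 = 118 HU, not scored.
- 350 HU plaque, 5 mm slice: (350 × 1.5 + 40 × 3.5) / 5 = 133 HU, scored.
- 300 HU plaque, 3 mm slice: (300 × 1.5 + 40 × 1.5) / 3 = 170 HU, scored.
- 300 HU plaque of 1.8 mm, 5 mm slice: (300 × 1.8 + 40 × 3.2) / 5 = 133.6 HU, scored.

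For a 1.5 mm plaque the threshold is reached at (130 × 5 − 140) / 1.5 = 340 HU on a 5 mm slice and at (130 × 3 − 60) / 1.5 = 220 HU on a 3 mm slice. Under these assumptions, only plaques between 220 and 340 HU change from missed to counted when the slice is thinned. This shows that the mechanism exists. It does not estimate its size in this study.

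**3. Effect on a within-patient test when true progression is zero**

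Assume a shift of b SDs of the paired difference and a two-sided 5% paired t-test. The rejection probability comes from the noncentral t distribution with n − 1 degrees of freedom and noncentrality b√n. Section 10.1 names no paired test, so the choice of test is also an assumption.

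| b | n = 20 | n = 40 |
|---|---|---|
| 0.1 | 7% | 10% |
| 0.25 | 19% | 34% |
| 0.5 | 57% | 87% |
| 1.0 | 99% | about 100% |

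On a ratio scale, if the old CT reads a fraction r of what the study CT would read, unchanged calcium shows an apparent change of 1/r − 1: +100% at r = 0.5, +25% at 0.8, −17% at 1.2 and −33% at 1.5.

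**4. Effect on a between-group comparison of change**

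An additive shift that is equal in both groups cancels. If the shift differs between groups by 0.1, 0.25, 0.5 or 1.0 SD, a 20 versus 20 t-test on change (38 degrees of freedom, noncentrality b√10) rejects in 6%, 12%, 34% or 87% of studies with no true difference.

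**The case against.** The strongest reply is that the decisive facts are not in the document. The protocol does not say that the old scans were contrast-enhanced, thick-sliced or ungated, and it names Agatston only for the new acquisition. Reading rules and the exclusion of unsuitable scans could sit in an SAP or imaging manual; only the protocol was available here. This stands in part. A reader might infer that a baseline score cannot validly be obtained from these scans at all, but the text does not support that. It supports only that comparability is asserted and not secured. An analysis plan could not restore it later without re-reading the scans by a common method or restricting to comparable ones.

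A reader might also infer that the neo-CRT versus surgery comparison is biased, because "neo-CRT has become standard treatment since 2012" would place surgery-alone patients in earlier scanner years. The documents do not establish this. The same paragraph of section 1 says that both treatments were given in that period, both groups are drawn from 2000-2012, and no treatment dates by group are given. Unequal error between groups is possible, not shown. Objective 4 as worded also names no between-group comparison.

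Finally, this is an exploratory pilot, CAC change is one of seven listed objectives, and the historical scans are the only baseline CTs the protocol names. That limits the weight of the point. It does not make the difference interpretable as calcium change.

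**Conclusion.** The point holds in a limited form. Objective 4 sets a score from unspecified pre-treatment diagnostic CTs against an Agatston score from a purpose-made CT, with no stated condition that would make them comparable. As written, the within-patient change and the baseline-risk use of CAC both mix calcium with measurement method.

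The direction and size are unknown. The densities, slice thicknesses, shifts and ratios above are assumed and only show what could happen. Objective 3 compares current scores obtained by one method and is not affected. The point should be corrected, but it does not undermine the study as a whole.

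**What to change.** - Keep the Agatston score for the current CT and objective 3.
- For objective 4 and the baseline-risk use, have the same reader score both CTs of each pair with one common ordinal visual score (for example 0-3 per coronary vessel, summed), without knowledge of treatment group. Make change in that score the objective 4 measure.
- Record contrast, gating and slice thickness of every baseline CT.
- Repeat the comparison in patients whose baseline CT was non-enhanced.
- Report any Agatston difference as descriptive only, with the difference in method declared.

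Cost: a change of protocol wording and one extra read of up to 40 existing scan pairs, with no new scan. The ordinal score is coarser than Agatston. It does not fully remove differences due to contrast and motion, and the protocol cites no evidence on how it performs across scan types, so the acquisition record and the restricted analysis are needed alongside it. The non-enhanced subset may be small.
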